- whether there are differences between the two groups in the volume of breast tissue removed.
- 2. whether diagnostic information obtained from a supine MRI is equivalent to that obtained from the prone MRI.

Section 3. ELIGIBILITY CRITERIA

Inclusion Criteria Phase 1

- 1. Age > 18 years
- 2. Histologic diagnosis of palpable invasive breast cancer or ductal carcinoma in situ
- 3. Patient desire to undergo breast surgery
- 3. Patients will have provided informed consent to participate, documented by their signature on the study consent form
- 4. The cancer enhances on breast MRI imaging.

Inclusion Criteria Phase 2

- 1. Age > 18 years
- 2. Histologic diagnosis of invasive breast cancer or ductal carcinoma in situ
- Determination by the surgeon that the neoplasm is non-palpable. A patient with a palpable hematoma from core biopsy, but a non-palpable neoplasm, will be eligible for study
- 6. Patient desire to undergo breast conserving surgery
- 7. Patients will have provided informed consent to participate, documented by their signature on the study consent form. The process of informed consent will be documented in the medical record and a copy of the signed consent form will be given to the patient.

Exclusion Criteria (Phases 1 and 2)

- Absolute contraindication to MRI, including presence of implanted electrical device (pacemaker or neurostimulator), aneurysm clip or metallic foreign body in or near eyes
- 2. Severe claustrophobia
- Contraindication to use of gadolinium based intravenous contrast, including life threatening allergy or compromised renal function (creatinine > 2.0)
- 4. History of median sternotomy
- 5. Pregnancy (Patient attestation that they are not pregnant will be acceptable, as per standard policy for MRIs at DHMC)
- 6. Multicentric breast cancer, defined as two or more tumors in different quadrants of the breast.

An eligibility worksheet will be completed for each patient prior to enrollment and will be signed and dated by the surgeon investigator.

Section 4. TREATMENT PLAN

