At the end of patient accrual, prone and supine MRIs from patients in Group S will be separately interpreted by two radiologists. The cases will be divided in halves. One radiologist will initially interpret half of the supine and half of the prone MRIs, the other will initially interpret the other half. After a 6-week interval, each Radiologist will interpret the other half of the images. Concerning lesions on each study will be identified, and then a comparison will be made between the supine and prone images to determine if lesions identified on the supine images are concordant with the number and size of lesions identified on the prone images.

Section 5. POTENTIAL TOXICITY

Supine MRIs are administered according to standard-of-care practice for prone breast MRI and represent no more additional risk than would be experienced by women receiving these exams as part of their (non-research) breast care. The risk of contrast enhanced MRI is very low, reflecting the minute risk of life threatening allergy and development of nephrogenic sclerosis related to gadolinium based intravenous contrast. Patients deemed to be at higher risk for gadolinium induced nephrogenic sclerosis because of compromised renal function will not be eligible for participation. Patients who experience a significant allergic reaction to gadolinium based intravenous contrast at the time of their clinical prone MRI will also be considered ineligible for study participation.

Optical scans will be performed using a GO!Scan 3D optical scanner (Creaform, Levis, Quebec, Canada). This scanner will be able to scan the entire breast in 1 minute. It uses white light (LED) to form the image, like a flashlight. There are no anticipated risks associated with the use of this scanner.

Section 6. DRUG FORMULATION AND PREPARATION

Not applicable.

Version 5.6.14

Sections 7 and 8. Clinical ENDPOINTS AND STATISTICAL ANALYSIS

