Our senior breast Pathologist, [name], has performed a detailed analysis of the surgical margins for patients who had a core biopsy which was positive for cancer or DCIS and then underwent partial mastectomy at Dartmouth in the year 2005. A total of 125 patients with invasive ductal carcinoma were identified: 31 (25%) had positive margins. Twenty six of 53 patients undergoing partial mastectomy for DCIS had positive margins (45%). Overall, 57/178 patients (32%) had positive margins. A two-thirds decrease in the positive margin rate (i.e., from 32% to 11 percent or less) would be clinically meaningful. The primary analysis will consist of computing the positive margin rate observed in the two groups and comparing them with a chi-squared test. Based on a chi-squared test with a significance level of 0.05 and a power of 80%, a sample size of 69 patients will be required in each group.

We will adopt a sequential testing procedure to assure that possible increases in the expected margin rate are detected. After 10% of the patients are enrolled, or 7 in each group, an exact test for proportions will be applied. If proportion of positive margins is greater than 32% and the p-value for the test is less than 0.004, the trial will be stopped as possibly increasing the rate. This procedure maintains the significance level at 0.05 and the power at 80% using Pocock boundaries for the Lan and Demets alpha spending function.[20]

Annually at Dartmouth we care for approximately 300 patients with invasive ductal cancer and 100 patients with DCIS. Approximately ²/₃ of these patients (266) will undergo breast conserving surgery. Approximately ³/₄ of these patients will have non-palpable tumors (200). We anticipate that it will be possible to accrue one third (67) of these patients per year. Thus, we expect that it will take 2 years to complete accrual.

Secondary endpoints will be analyzed as follows. The mean specimen volume from Group S will be compared to the mean specimen volume from Group W using t - statistics. The concordance between lesion volumes identified on the supine MRI images and the prone MRI images will be evaluated through correlation and regression analysis.

Relevant data will be saved in Velos case report forms. The NCCC Safety and Data Monitoring Committee will monitor this trial quarterly.

Section 9. HUMAN SUBJECTS

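### The supine/prone MRI equivalence objective has no rule for concluding equivalence: only lesion volumes are analysed, by correlation and regression without a criterion, and lesion number has no statistic

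*Combined protocol and SAP*

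**What the plan says.** The combined protocol and SAP treats this objective in three places.

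- **Section 2 (Objectives), secondary objective 2:** to determine "whether diagnostic information obtained from a supine MRI is equivalent to that obtained from the prone MRI".
- **Section 4 (Treatment Plan):** after accrual, "prone and supine MRIs from patients in Group S will be separately interpreted by two radiologists". "Concerning lesions on each study will be identified", and the comparison asks whether "lesions identified on the supine images are concordant with the number and size of lesions identified on the prone images". Each radiologist reads one half first; then "After a 6-week interval, each Radiologist will interpret the other half of the images". Every image therefore ends with two readings.
- **Sections 7 and 8 (Clinical Endpoints and Statistical Analysis):** "The concordance between lesion volumes identified on the supine MRI images and the prone MRI images will be evaluated through correlation and regression analysis".

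No section gives an equivalence margin, limits of agreement, a target correlation, slope or intercept, a statistic for lesion number, a rule for matching lesions, or a statement of how the two readings are combined. The analysis sentence is complete, so redaction does not explain the gap. Phase 1, by contrast, has an explicit acceptance rule: all four image-guided edge measurements within 1 cm of palpation.

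**The concern.** Objective 2 asks a yes/no question, and the analysis supplies no way to answer it. There are three gaps.

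1. Correlation measures how closely volumes rise and fall together, not whether they are the same.
2. Regression carries information about bias, but nothing says which slope or intercept would be acceptable.
3. Number is half of the Section 4 comparison and is absent from the statistical section. A lesion visible on one scan only has no partner volume, and the plan is silent on its handling.

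At stake is whether the report can justify a statement that supine MRI gives the same diagnostic information as prone MRI. A high correlation could be offered in support of that statement when it does not bear on it.

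**Working it through.** **The plan's own figure.** There is no sample size, power or margin for this objective. The only relevant number is 69 per group, set for the positive-margin rate, which limits Group S to about 69 pairs. It reproduces. With 32% v 11%, two-sided 0.05 and 80% power:

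- n₀ = [1.96√(2×0.215×0.785) + 0.842√(0.32×0.68 + 0.11×0.89)]² / 0.21² = 58.9
- with continuity correction, (58.9/4)[1 + √(1 + 4/(58.9×0.21))]² = 68.1, rounded up to 69

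That figure is not in dispute.

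**Correlation: algebra.** If supine volume is b times prone volume apart from random error, b cancels from r on the raw scale. On the log scale it becomes an added constant, which r also ignores.

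**Correlation: illustration.** The assumptions are the reviewer's; none is in the documents. One lesion per patient, one reading per scan, log-normal true volumes with log SD s, and log measurement error SD e. Then r = s/√(s²+e²) with error on supine only, and r = s²/(s²+e²) with error on both scans.

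| s | supine only, e=0.15 | supine only, e=0.30 | both, e=0.15 | both, e=0.30 |
|---|---|---|---|---|
| 0.5 | 0.96 | 0.86 | 0.92 | 0.73 |
| 1.0 | 0.99 | 0.96 | 0.98 | 0.92 |
| 1.5 | 0.99 | 0.98 | 0.99 | 0.96 |

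Every entry holds for b = 1, 0.9, 0.7 or 0.5. The level of r reflects spread and error, not bias.

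**Regression of raw supine on raw prone volume, same assumptions.** With error on supine only, slope = b·exp(e²/2). With error on both, slope = b·exp(e²)[exp(2s²) − exp(s²)] / [exp(2(s²+e²)) − exp(s²+e²)].

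- No bias: highest 1 × exp(0.045) = 1.05. Lowest, at s=0.5 and e=0.30 on both, 1.094×(1.649−1.284)/(1.974−1.405) = 0.70.
- Multiplying by b, 10% smaller gives 0.63 to 0.94, 30% smaller 0.49 to 0.73, and halved 0.35 to 0.52.

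Halving is therefore separated from no bias. Smaller differences are not: a slope near 0.70 fits both no bias with noisy prone volumes and volumes 30% smaller with error on supine only (0.7×exp(0.011) = 0.71).

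**Number.** Suppose supine missed 14 of 69 prone lesions at random and these were left out of the volume analysis. The expected r of the other 55 would not change. The detection proportion shows the loss directly: 55/69 = 80%, exact 95% CI 68% to 88%.

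**A criterion on the mean ratio alone would not be enough.** Take no bias and e=0.30 on both scans:

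- SD of log differences = 0.30√2 = 0.424.
- 95% CI of the mean ratio, 69 pairs: multiply or divide by exp(1.995×0.424/√69) = 1.11.
- Limits of agreement: exp(±1.96×0.424) = 0.44 to 2.30.
- Against a purely illustrative margin of 0.80 to 1.25, the CI falls inside in about 98% of trials. Yet the share of individual pairs outside it is 2[1 − Φ(0.223/0.424)], about 60%.

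A size rule therefore has to cover the limits of agreement as well as the mean.

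**The case against.** **The planned regression is not blind.** This stands. A reader might infer that the analysis can neither support nor reject equivalence. The documents do not support that: gross non-equivalence in size, such as halved volumes, would be visible in the slope. What is missing is a rule for reading it.

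**Unmatched lesions may not be lost.** This also stands. A reader might infer that lesions seen on one scan only are dropped. The plan does not say so; zero volumes or per-patient totals are possible. The fault is that handling is unspecified.

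**Multicentric disease is excluded.** Section 3 excludes "Multicentric breast cancer, defined as two or more tumors in different quadrants of the breast". This reduces ambiguity in pairing but does not remove it: two lesions in one quadrant remain eligible, and Section 4 compares all concerning lesions.

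**The aim may have been descriptive.** Sections 4, 7 and 8 speak of concordance; only Section 2 speaks of equivalence. That is a fair reading, and rewording objective 2 would be a legitimate remedy. It does not rescue correlation as the agreement measure, and it leaves number without a statistic.

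**It is only a secondary objective, read after accrual.** True, and this limits the importance of the point.

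**Conclusion.** The point holds. The plan poses an equivalence question about lesion number and size, analyses volume only, and sets no rule for concluding equivalence. Insensitivity of correlation to proportional bias is algebra and needs no assumption. The absence of a criterion, of a number statistic and of a rule for unmatched lesions can be read directly from the text.

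The numerical ranges are illustrative. They rest on assumed log-normal volumes, log SD 0.5 to 1.5, error SD 0.15 to 0.30, one lesion per patient and one reading per scan. They show the kind of ambiguity, not its size in this trial.

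A reader might carry the point over to the primary result or the sample size. Nothing supports that: the positive-margin comparison and the 69 per group are unaffected. This is a worthwhile, inexpensive correction to a secondary objective.

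**What to change.** Replace the correlation-and-regression sentence in Sections 7 and 8 with:

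1. **Size.** A log-scale Bland-Altman analysis giving the supine/prone geometric mean ratio and 95% limits of agreement, with confidence intervals. Conclude equivalence in size only if both the CI of the mean ratio and the limits of agreement lie within bounds the investigators fix before the readings.
2. **Number.** The proportion of prone lesions found on supine, and the reverse, with 95% CIs that allow for several lesions per patient. Fix a matching rule before the readings, count unmatched lesions as disagreements, and fix a minimum acceptable lower confidence limit.
3. **Supporting text.** Keep correlation and regression as descriptive, and state how the two readings per image are used.

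If the investigators prefer not to set bounds, report the same measures and reword objective 2 as descriptive, with no conclusion of equivalence.

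**Cost.** SAP wording and a little analysis. Bounds and a matching rule must be named in advance, which is feasible because reading follows accrual. Lesion location must be recorded at the planned readings, since Section 4 names only number and size. If measurement error is large, or the bounds narrow, the result may be inconclusive.

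### The supine/prone lesion-volume analysis does not say how two readings, or several lesions, per patient are handled, and it names no estimate of the volume difference

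*Combined protocol and SAP*

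**What the plan says.** Section 2 lists as a secondary objective to determine "whether diagnostic information obtained from a supine MRI is equivalent to that obtained from the prone MRI".

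The reading scheme is in Section 4. After accrual ends, "prone and supine MRIs from patients in Group S will be separately interpreted by two radiologists". The work is split in two sessions: "One radiologist will initially interpret half of the supine and half of the prone MRIs, the other will initially interpret the other half". Then: "After a 6-week interval, each Radiologist will interpret the other half of the images." By the end, every Group S scan has been read by both radiologists. The comparison is whether supine findings are "concordant with the number and size of lesions identified on the prone images", so more than one lesion in a patient is foreseen.

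Section 3 limits this by excluding "Multicentric breast cancer, defined as two or more tumors in different quadrants of the breast". It does not exclude several foci in one quadrant, contralateral findings, or concerning lesions that prove benign.

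Sections 7 and 8 give one sentence of analysis for this objective: "The concordance between lesion volumes identified on the supine MRI images and the prone MRI images will be evaluated through correlation and regression analysis." Nothing else in the document says how the readings are analysed.

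**The concern.** Two readings of the same pair of scans share the patient, the lesion and whatever the change of position did to that breast. Two lesions in one patient share much of this as well. Such pairs should be expected to be positively correlated, so 138 of them carry less information than 138 patients would. The planned sentence takes the lesion volume as its subject and does not say whether the unit is the patient, the lesion or the reading. An analyst could pool all pairs and still comply with it.

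The quantity estimated is also a problem. The objective is equivalence, which asks how far supine volumes differ from prone volumes. A correlation does not answer that: if every supine volume were the same fixed multiple of its prone volume, the correlation would be 1 whatever the multiple. A slope and intercept say more, but reading error in the prone volume flattens the slope even when the two positions agree on average. Overstated precision would favour the conclusion that the objective hopes to reach.

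**Working it through.** **Inputs.** Group S size: "a sample size of 69 patients will be required in each group" (Sections 7 and 8). Readers per scan: 2 (Section 4). Scans per patient: 2. The documents give neither the within-patient correlation nor the number of lesions per patient, so both are assumed over a range.

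**The plan's own figure.** With rates of 32% and 11%, two-sided alpha 0.05 and 80% power, the mean rate is 0.215 and

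n = [1.96·√(2·0.215·0.785) + 0.842·√(0.32·0.68 + 0.11·0.89)]² / 0.21² ≈ 59.

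The continuity correction raises this to 69, matching the plan. That figure sizes the primary endpoint. No precision is stated for the supine/prone comparison.

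**Number of readings.** 69 × 2 scans × 2 readers = 276 readings, or 138 reader-level supine/prone pairs from 69 patients with one lesion each.

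**Mean difference, if pairs are pooled.** Let ρ be the correlation between the two readers' supine-minus-prone differences in one patient. The true variance of the mean is (1 + ρ) times the naive one, so coverage of a nominal 95% interval is 2Φ(1.96/√(1 + ρ)) − 1.

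| Assumed ρ | √(1 + ρ) | Coverage |
|---|---|---|
| 0.3 | 1.14 | 91.4% |
| 0.5 | 1.22 | 89.0% |
| 0.8 | 1.34 | 85.6% |

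At ρ = 0.5 the effective number of pairs is 138/1.5 = 92.

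**Slope, if pairs are pooled.** The standard error is too small by about √(1 + ρx·ρe), where ρx is the within-patient correlation of the prone volumes and ρe that of the regression residuals. With ρx = 0.8 and ρe = 0.5 this is √1.40 = 1.18, against 1.22 for the mean difference at ρ = 0.5. A simulation of 69 patients with two pairs each and a true correlation of 0.8 gave:

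| Assumed ρe | Slope coverage, ρx = 0.8 | Slope coverage, ρx = 0.95 |
|---|---|---|
| 0 | 95.0% | 95.0% |
| 0.25 | 92.5% | 92.5% |
| 0.5 | 90.3% | 89.3% |
| 0.75 | 87.3% | 86.5% |

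With four pairs per patient (for example two readers and two lesions), ρx = 0.8 and ρe = 0.75, slope coverage fell to 76%. Analysing patient means held it at about 95% throughout.

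**Correlation coefficient.** For r = 0.8, the Fisher-z 95% interval is 0.731 to 0.853 if 138 pairs are taken as independent, and 0.695 to 0.872 with 69. The second is the limit where the second reader adds no information. In the simulation the pooled Fisher-z interval covered only 92 to 93% even at ρe = 0, because the prone volumes are themselves correlated within patient.

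**The case against.** The strongest reply is that the plan does not commit the error. A reader might infer that repeated readings will count as independent pairs and that the intervals are therefore too narrow. The text does not support that. It names correlation and regression without saying ordinary, pooled or independent. Averaging the readers, analysing each reader separately or fitting a mixed model would all fit it. With one lesion per patient, the first two give no understatement. The sentence also specifies no confidence interval, test or equivalence margin. This stands, and it makes the coverage figures conditional.

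The mean-difference figures are also for a quantity that the plan does not name, and the slope is affected less. That stands too. The mean difference is still the relevant scale, because it is what an equivalence objective needs.

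A second tempting reading is that, without a between-reader comparison, a supine/prone difference could not be told apart from reader variation. That goes too far. Each radiologist reads both positions in every patient, so a constant reader bias cancels and random reading noise is already in the spread of the paired differences. The between-reader ratio helps to judge whether a difference is large, but a valid test does not depend on it.

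Finally, excluding multicentric cancer limits the number of lesions per patient. The four-pair result is therefore an illustration and not an expectation.

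What remains is that the sentence leaves the unit, the handling of readers and the estimand open, so choices that give different precision could be made after the data are seen.

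**Conclusion.** The concern holds as an omission with a conditional consequence. Section 4 yields clustered, doubly read data, while Sections 7 and 8 give an analysis with no stated unit, no treatment of clustering and no estimate of the supine/prone volume difference. If pairs are pooled, a nominal 95% interval for the mean difference covers roughly 86% to 91%. This rests on one lesion per patient, 69 patients and assumed correlations of 0.3 to 0.8. The slope suffers somewhat less and is unaffected if residuals are uncorrelated between readers.

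Only a secondary objective is affected. The primary comparison of positive margin rates, the 69 per group and the stopping rule do not depend on it. The change is worth making because it is cheap and the readings do not start until accrual ends.

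**What to change.** Replace the sentence in Sections 7 and 8 with a short specification:

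- **Matching.** State beforehand the rule by which a lesion on the supine images is paired with one on the prone images.
- **Estimate.** For matched lesions, estimate the supine/prone volume ratio on the log scale.
- **Interval.** Give a 95% interval from a bootstrap that resamples patients, or from a model clustered on patient. Reader should be a fixed effect, since two readers are too few to estimate a reader variance.
- **Yardstick.** Report the between-reader volume ratio on the same scans beside it.
- **Unmatched lesions.** Report lesions seen in one position only separately, as concordance in number. They have no log volume in the other position, so a volume model would drop the discordant findings that Section 4 sets out to find.

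The correlation may stay as a description. No new scans, readings, readers or patients are needed. The cost is analysis wording, a little programming and slightly wider intervals than a pooled analysis would show.
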